The *de facto* estimand will include all available CAPS-5 outcome data from all participants in the mITT set regardless of adherence to the treatment, including CAPS-5 data collected after treatment discontinuation in case of early termination. This will be estimated in the mITT set by a statistical comparison between treatment groups using the MMRM model with a weighted least squares estimate of the change in CAPS-5 scores from baseline to 18 weeks after randomization across all the post treatment CAPS-5 measures. The sponsor expects no more than 5% of the participants will discontinue treatment after the first experimental session and CAPS-5 outcome assessment, due to the highly-controlled treatment setting which is analogous to residential or in-patient treatment settings. Additionally, some participants may choose to discontinue after the first experimental session because of strong and early positive response. These participants are treatment successes and should not be modeled as treatment failures. Using the least squares estimate of the mean reduction in CAPS-5 scores across all treatment sessions will capture these early successes in the *de facto* estimand. It can be argued that because all participants in the study will have continued data collection and all observed post-treatment CAPS-5 scores included in the *de facto* estimand that there is no missing data in this analysis. Thus the *de facto* estimand will support the primary *de jure* estimand.

1. The choice of primary estimand will be tested with a supportive analysis including a different estimand:
 - a. To determine *de facto* effectiveness by comparing MDMA-assisted psychotherapy to identical psychotherapy with inactive placebo for PTSD, as measured by the estimand of change in CAPS-5 Total Severity Score from Baseline after 18 weeks post-randomization, including all observed data after early termination.
2. The effect of departures from choices and assumptions made for the primary analysis will be tested as sensitivity analyses for the primary estimand. No sensitivity analyses will be performed for the secondary efficacy endpoints. Details of the sensitivity analyses with multiple imputation will be provided in the Final SAP.
 - a. Distributional assumptions for the full data will be tested, if distribution found not to be normal, we will test a transformation of the data, such as the log transformation, to achieve normality.

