8.7.3 Key Secondary Efficacy Analyses

For the key secondary analysis of efficacy, the de jure estimand will be used to estimate the causal effect of MDMA-assisted psychotherapy on PTSD on the SDS in the intended population of patients with PTSD from any cause (Estimand 3 in Table 4). The SDS is a 3-item scale measuring the severity of disability in the domains of work, family life/home responsibilities and social/leisure activities. Each of these three domains is scored on a ten-point Likert scale, where a score of 0 is ‘not at all impaired’, 5 is ‘moderately impaired’ and 10 is ‘very severely impaired’. The summary measure used to analyze the treatment effect on SDS will be the mean of the 3 item responses at each visit. Any participant who did not work during the reporting period due to reasons related to PTSD will be scored as a 10 on item 1. In cases where participants did not work due to reasons unrelated to PTSD, the score for item 1 (work/school) will be imputed by averaging the scores of items 2 and 3. It is expected that no more than 5% of participants will have item 1 (work/school) imputed, based on prior studies of paroxetine with PTSD. To limit missing data and ensure standardized administration, the SDS will be administered in a clinician-rated format during the same visits as the CAPS-5 by the centralized Independent Rater Pool. The clinician-rated administration will be important in limiting misinterpretation of the Work/school Impairment item that could contribute to elevated rates of skipping out, which can also be completed in reference to school, unpaid or volunteer work, and may not immediately come to mind in a participant-reported format.

If item 1 of the SDS is imputed in more than 5% of the participants, multiple imputation methods will be explored as an additional sensitivity analyses. If more than 5% of Item 1 data is missing, the frequency of participants not working due to reasons unrelated to PTSD and related to PTSD will be tabulated for both overall and within each visit. Additionally, a sensitivity analysis will be conducted to explore the effect of the different distributions for average SDS depending on whether the respective checkboxes for item 1 are checked or not. Separate MMRM models for the two types of responses to item 1 will be run and the treatment effect will be the weighted average of the two groups with the weights calculated as the frequency of checked item 1’s.

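### The planned SDS sensitivity analysis that splits the MMRM by the item 1 checkbox does not estimate the randomized effect if treatment changes the box, so it cannot test the robustness of the key secondary result

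*SAP*

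**What the plan says.** SAP 8.7.3 defines the key secondary outcome visit by visit: "The summary measure used to analyze the treatment effect on SDS will be the mean of the 3 item responses at each visit". Two rules cover people who did not work. If the reason was PTSD, the rule is explicit: "Any participant who did not work during the reporting period due to reasons related to PTSD will be scored as a 10 on item 1". If the reason was something else, item 1 "will be imputed by averaging the scores of items 2 and 3".

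The same section expects item 1 to be imputed in at most 5% of participants. Above 5% imputed, multiple imputation is to be explored. Above 5% missing, the two reasons for not working are to be tabulated overall and by visit. A further analysis then looks at how average SDS differs "depending on whether the respective checkboxes for item 1 are checked or not". For that analysis, "Separate MMRM models for the two types of responses to item 1 will be run", and the reported effect is "the weighted average of the two groups with the weights calculated as the frequency of checked item" 1 responses.

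The modelled visits are 8, 13 and 19, all after randomization. The confirmatory SDS analysis, specified later in 8.7.3, is one MMRM on all mITT participants at two-sided alpha 0.0499, with no split. SAP 8.7.2, however, states: "No sensitivity analyses will be performed for the secondary efficacy endpoints".

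**The concern.** A subgroup analysis keeps the protection of randomization only if the subgroup is fixed before treatment can act on it. Here the score is defined per visit, the box belongs to the score, and the tabulation just before the split is per visit. No baseline classification is mentioned, so the natural reading is a box recorded after randomization.

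The PTSD-related box is also a component of the outcome, because checking it fixes one of the three items at its maximum. The trial has reason to expect treatment to affect this domain: Protocol 2.2.1 lists inability to keep a job among the consequences of PTSD, and both documents plan a between-group comparison of workplace productivity. The documents do not show that treatment changes the box, but they make it plausible.

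If it does, the people who check the box on MDMA are not comparable with those who check it on placebo, and neither are those who leave it blank. If classification is per visit, one participant's repeated measures can also be divided between the two models. What is at stake is interpretation. A gap between the split result and the main result could reflect the scoring of item 1 or only the conditioning, and nobody could tell which.

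**Working it through.** **Plan's own figures.** The documents give no SDS effect, SD, checkbox rate or power, so there is no plan figure to reproduce on this point. The only stated power, 90% for CAPS, does reproduce. The difference is 37.4 − 20.5 = 16.9, the variance 335 + 280 = 615, with 47 per arm. Then 16.9 / √(2 × 615 / 47) = 3.30, and 3.30 − 1.96 = 1.34, which gives power of about 0.91. It does not bear on the SDS.

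**What the weighted average leaves out.** Let p_M and p_P be the proportions checked on MDMA and placebo, and Δc and Δu the treatment differences within checked and unchecked. With 1:1 allocation, the pooled share is p̄ = (p_M + p_P)/2. For unadjusted means,

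total effect = [p̄ Δc + (1 − p̄) Δu] + (p_M − p_P) × G,

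where G is the checked-minus-unchecked gap in mean SDS change, averaged over arms. The bracket is the split analysis with pooled weights. The last term is the benefit from moving people between categories, and the split drops it. It is zero when p_M = p_P. That holds when treatment has no effect, when treatment does not change the box, and, in expectation, when the box is taken at baseline.

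**Simulation under assumed values.** There were 20,000 participants per arm. The unstructured-covariance MMRM on change in mean SDS had baseline SDS as covariate, was fitted by maximum likelihood, and left out site and dissociative subtype. All SDS means, SDs, effects and box rates are assumptions. The split below is on the PTSD-related box at Visit 19.

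| Assumed effect | Box at V19, MDMA / placebo | Unsplit MMRM | Δc | Δu | p̄ | Weighted average | Shrinkage |
|---|---|---|---|---|---|---|---|
| about 1 | 15% / 22% | −1.03 | −0.59 | −0.93 | 0.19 | −0.86 | 17% |
| about 2 | 4% / 10% | −1.98 | −1.14 | −1.86 | 0.07 | −1.81 | 8% |
| about 2 | 10% / 22% | −2.04 | −1.17 | −1.84 | 0.16 | −1.73 | 15% |
| about 3 | 2% / 10% | −2.91 | −1.82 | −2.75 | 0.06 | −2.70 | 7% |
| about 3 | 6% / 22% | −2.97 | −1.74 | −2.66 | 0.14 | −2.53 | 15% |
| about 2, box not changed by treatment | 30% / 30% | −1.76 | −1.26 | −1.96 | 0.30 | −1.75 | under 1% |

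Percentages come from unrounded values.

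Worked line (third row): 0.16 × (−1.17) + 0.84 × (−1.84) = −0.19 − 1.55 = −1.73. Against −2.04 that is a loss of 0.31, and 0.31 / 2.04 = 15%. The identity above agrees, approximately because the model adjusts for baseline: 0.31 / (0.22 − 0.10) gives G of about 2.6 points.

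Same scenario, split on the Visit 3 box: 0.32 × (−2.09) + 0.68 × (−2.02) = −2.04, so nothing is lost.

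**Range over definitions of the split, where treatment changes the PTSD-related box.**

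- PTSD-related box at Visit 19, or per visit: 7 to 17% (0.10 to 0.44 points).
- PTSD-related box ever checked after baseline: 5 to 8%.
- Any box at Visit 19: 3 to 13%.
- Baseline box, or only an unrelated-reason box independent of treatment: at most 0.02 points.

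Every material bias was toward the null.

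**The case against.** The strongest reply is that nothing confirmatory depends on this analysis. It is exploratory, conditional on a trigger, and attached to no decision rule. That stands. A reader might infer that the key secondary effect itself is biased, or that its error rate is at risk. The documents do not support that: the tested SDS model is a single unsplit MMRM, and the split shows no bias when treatment has no effect.

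Second, the trigger may not fire. A reader might infer that severe PTSD makes it likely. But PTSD-related non-work is scored 10 and so is not missing. The 5% threshold most naturally concerns unrelated non-work or skipped items, and the SAP uses clinician-rated administration to limit skipping. This stands too: the documents do not show that the trigger is likely.

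Third, the text does not name the classifying visit, say which boxes form the two types of response, or say whether weights are pooled or by arm. A baseline box, or an unrelated-reason box independent of treatment, would give no material bias. That is correct, but the SAP does not say either, and its per-visit wording points the other way.

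Fourth, bias toward the null is conservative. That prevents false support, but a real effect could look fragile for reasons unrelated to item 1 scoring.

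Finally, multiple imputation is already planned. That is true and is the better check, although the SAP says only that such methods will be explored.

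**Conclusion.** The point holds for the triggered sensitivity analysis only. On the plain reading, SAP 8.7.3 conditions on a post-randomization response that is built into the SDS score. If treatment changes that response, the frequency-weighted average is not the effect of the randomized treatments that the section sets out to estimate, and it cannot serve as a robustness check.

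The size is not fixed by the documents. Under the assumed effects (about 1 to 3 points) and PTSD-related box rates at Visit 19 (10 to 22% on placebo, 2 to 15% on MDMA), shrinkage is about 3 to 17% toward the null, depending on the box and visit used. A reader might infer a loss of a quarter or more. No figure in the documents supports that, and the largest loss in these scenarios was 17%.

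This is more than missing detail, because the rule as it most naturally reads would give a misleading check. SAP 8.7.2 adds a separate contradiction, since taken literally it means the split would not be run at all.

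**What to change.** Preferred: drop the split, keep all participants in one MMRM with the confirmatory specification, and vary only how item 1 is handled.

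- Make the planned multiple imputation specific. State which item 1 values are imputed, and impute by arm from items 2 and 3, CAPS-5 and earlier visits.
- In addition or instead, use the mean of items 2 and 3 for everyone as a sensitivity score. The cost is that this analysis leaves out the work domain.

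Alternative, if a split is wanted: define the strata by the Visit 3 checkbox, name the box or boxes, and pool the weights over arms. This is unbiased, but the checked stratum may be small. At the assumed baseline rates of 17 to 32%, it would hold 17 to 32 of 100 participants, which is few for an unstructured MMRM with site effects.

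In either case, amend the sentence in SAP 8.7.2 so that it allows the SDS sensitivity analyses that 8.7.3 describes. The change is to SAP wording only. It needs no new data and leaves the confirmatory test as it is.

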8.7.4 Responder Analyses

The CAPS-5 produces a Total Severity Score based on severity of PTSD symptom domains described in the DSM-5, as well as a categorical rating indicating whether a participant meets PTSD diagnostic criteria. A psychometric validation study found the following severity score ranges for the CAPS-5: Asymptomatic (0-10), Mild (11-22), Moderate (23-34), Severe (35-46), Extreme (47+). Based on these data, a 10-point reduction in CAPS-5 Total Severity Score is clinically meaningful. As an alternate definition of treatment response to assess clinical significance of study outcomes, the sponsor will conduct a responder analysis to support findings from the primary efficacy analysis, and to explore how many single-dose treatments are needed to achieve response (See Figure 1). A similar responder analysis will be conducted for overall change in SDS item scores.

Figure 1: CONSORT for PTSD Responder Analysis After Treatment

[figure not shown]

[1] Response at T2, T3, and T4 will be in comparison to Baseline at T1.

The sponsor will measure changes in functional impairment with the SDS throughout treatment at the same visits as the CAPS-5 in this study. The authors of the SDS have provided the following

score ranges to describe functional impairment severity for each of three items describing the functional domains of work, social life, and family life: No impairment (0), Mild impairment (1-3), Moderate impairment (4-6), Marked impairment (7-9), Extreme impairment (10). Based on the psychometric development publication [5] and prior Paroxetine studies for treatment of PTSD, a 4-point mean reduction across SDS items would represent a clinically meaningful treatment response, as this would correspond to downward change from Extreme to Moderate, Marked to Moderate, or Moderate to Mild in severity of any domain of functional impairment. If a participant drops to a mean score of less than 3 across SDS items, this would be defined as a functional remission indicating Mild or No impairment.

Figure 2: CONSORT for Functional Impairment Responder Analysis After Treatment

[1] Response at T2, T3, and T4 will be in comparison to Baseline at T1.

As an alternate definition of treatment response to assess clinical significance of study outcomes, the sponsor will conduct an exploratory responder analysis to support findings from the key secondary efficacy analysis, to explore the onset of clinically meaningful functional improvement (Figure 2). To further support the exploration of a clinically meaningful functional improvement in the PTSD population, results will be plotted in a cumulative distribution function plot to examine the magnitude of differences between treatment groups. Distribution-based methods including standard error of measurement (SEM) and one standard deviation away from the mean SDS scores at baseline will be reported. Ceiling effects will be assessed based on 40% of responses at most endorsing Extreme Impairment and floor effects will be assessed based on less than 5% of responses endorsing No Impairment on each item.

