7.2 Secondary Measure

7.2.1 SDS (Sheehan Disability Scale)

The SDS is a clinician-rated assessment of functional impairment [63]. The items indicate degree of impairment in the domains of work/school, social life, and home life, with response options based on an eleven-point scale (0=not at all to 10=extremely), and five verbal tags (not at all, mildly, moderately, markedly, extremely). The SDS takes 1 to 2 minutes to complete. The measure can be scored for each of the three domains. The SDS has high internal consistency and accurately identified 80% of a sample of primary care patients with mental disorders [64].

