14.2.1.3 Exploratory Secondary Outcomes

Longitudinal CAPS-5 Total Severity Score and SDS item scores will be plotted across visits to characterize the onset of treatment effect. Cohen's d IGPP effect size of MDMA will be estimated using Cohen's techniques.

An exploratory responder analysis will further characterize clinical significance of PTSD treatment effect in the mITT set after each Experimental Session based on the following categories:

- Treatment Response: 10-point or greater reduction in CAPS-5 Total Severity Score
- Loss of Diagnosis: 10-point or greater reduction in CAPS-5 Total Severity Score and no longer meeting PTSD diagnostic criteria on CAPS-5
- Remission: CAPS-5 Total Severity Score of 11 or less and no longer meeting PTSD diagnostic criteria on CAPS-5

Exploratory sub-group analyses may be conducted when possible to evaluate efficacy by treatment group and individual demographic characteristics (e.g., age, gender, ethnicity, index trauma, dissociative subtype of PTSD, presence of secondary traumatic stressors during the assessment period with LEC-5, medication tapering, diagnosis of comorbid depression, diagnosis of comorbid psychiatric diagnosis, and number of Experimental Sessions completed). Exploratory analyses of secondary outcome measures will be described in the Statistical Analysis Plan.

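### The SDS functional-remission rule (item mean below 3) does not guarantee the mild-or-no-impairment label that the SAP attaches to it

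*SAP*

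**What the plan says.** SAP 8.7.4 takes its SDS severity categories from the authors of the scale and describes them as "score ranges to describe functional impairment severity for each of three items describing the functional domains of work, social life, and family life". The categories are "No impairment (0), Mild impairment (1-3), Moderate impairment (4-6), Marked impairment (7-9), Extreme impairment (10"). A few lines later the SAP defines remission on the average of the items: "If a participant drops to a mean score of less than 3 across SDS items, this would be defined as a functional remission". The same sentence goes on to say that such a score means impairment is mild or absent.

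Three other places bear on this:

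- Protocol 7.2.1 gives each item "response options based on an eleven-point scale (0=not at all to 10=extremely"), so items are whole numbers from 0 to 10.
- SAP 8.7.3 fixes the summary: "The summary measure used to analyze the treatment effect on SDS will be the mean of the 3 item responses at each visit".
- SAP 8.7.3 also has two rules for item 1 (work/school). A participant who did not work because of PTSD is scored 10. A participant who did not work for other reasons gets the average of items 2 and 3.

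For the CAPS-5, Protocol 14.2.1.3 defines "Remission: CAPS-5 Total Severity Score of 11 or less and no longer meeting PTSD diagnostic criteria on CAPS-5". SAP 8.7.4 bands scores of 0 to 10 as Asymptomatic and 11 to 22 as Mild.

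**The concern.** The bands describe single domains, but the remission rule averages across domains. An average can be low while one domain is high. A participant can therefore be counted as a functional remitter, under a label saying mild or no impairment, with Moderate or Marked impairment in work, social life or family life. Conversely, someone who is Mild in every domain can fail the rule.

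SAP 8.7.4 presents the responder analyses as a way to judge the clinical significance of the results, with the SDS version supporting the key secondary analysis. A reader of the study report would take a remission rate described in those words literally. What is at stake is the meaning of that one reported rate, not any hypothesis test.

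**Working it through.** **Inputs.** Three items, each a whole number from 0 to 10 (Protocol 7.2.1); item bands and the mean-below-3 rule (SAP 8.7.4); item 1 rules (SAP 8.7.3).

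**Step 1: restate the rule.** With whole-number items, mean < 3 is the same as sum ≤ 8.

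**Step 2: count the qualifying patterns.** There are 11³ = 1,331 ordered patterns. Those with sum ≤ 8 number C(11,3) = 165.

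**Step 3: count the patterns that satisfy the label.** All three items at 3 or below gives 4³ = 64 patterns. Only 3/3/3 has a sum above 8 (sum 9, mean 3.00). So 64 − 1 = 63 of the 165 patterns have every domain at Mild or none, and 165 − 63 = 102 do not.

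**Step 4: classify the 102 by their highest item.** The other two items must sum to no more than 8 minus that item.

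| Highest item | Band | Patterns |
|---|---|---|
| 4 | Moderate | 3 × 15 − 3 = 42 (4/4/0 and its orderings would otherwise count twice) |
| 5 | Moderate | 3 × 10 = 30 |
| 6 | Moderate | 3 × 6 = 18 |
| 7 | Marked | 3 × 3 = 9 |
| 8 | Marked | 3 × 1 = 3 |

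Moderate: 42 + 30 + 18 = 90. Marked: 9 + 3 = 12. Total: 102. The Marked patterns are 7/0/0 (mean 2.33), 7/1/0 (2.67) and 8/0/0 (2.67), in any order. The highest single item compatible with remission is 8, so an Extreme domain cannot occur.

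**Step 5: apply the item 1 rules.**

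- Item 1 scored 10: the mean is at least 10/3 = 3.33, so remission is impossible.
- Item 1 imputed as (a + b)/2 from items 2 and 3: the mean is [(a + b)/2 + a + b]/3 = (a + b)/2. Remission needs a + b ≤ 5, so the highest possible item is 5 (Moderate). Of the 21 qualifying pairs, 6 contain a Moderate item (4/0, 4/1 and 5/0, in either order). Marked cannot be reached.

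**Step 6: CAPS-5.** Of the 12 whole-number scores from 0 to 11, 11 fall in the SAP's Asymptomatic band and one, the score of 11, falls in Mild.

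**The case against.** The strongest reply is that the label describes the mean, not each item. The mean is the prespecified summary measure, and the remission sentence speaks of a mean score. Read that way, a mean below 3 does sit at Mild or lower. But the SAP assigns the bands to items, and its preceding sentence on a 4-point response also speaks of category changes in individual domains. The bands are whole-number ranges, so means such as 0.33 (1/0/0) fall in none of them. Even on the mean reading, a mean of exactly 3.00 is the top of Mild and yet fails the rule. At best the label is ambiguous. The content of Figure 2 is not visible, so it cannot settle the matter.

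A second reply is that lopsided patterns should be uncommon. Protocol 7.2.1 reports high internal consistency, 72 of the 102 patterns (42 + 30) peak at 4 or 5, and only 12 of 165 reach Marked. This stands as a caution about size. A reader might take 102/165 = 62% as a misclassification rate. It is not one, because it weights every pattern equally and the documents give no item-level data.

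A third reply also stands: the work rule already bars remission for anyone scored 10 on item 1, so the most obvious work-disability error is blocked.

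Finally, a reader might infer that the CAPS-5 remission definition contradicts its own severity bands too. The documents do not show that. The protocol's definition cites no band, does not equate remission with being asymptomatic, and also requires loss of diagnosis. The visible text of SAP 8.7.4 uses the CAPS-5 bands to justify a 10-point response and gives no CAPS-5 remission cut-off; Figure 1 is not shown.

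**Conclusion.** The SDS point holds. Under the item bands in SAP 8.7.4, a mean below 3 neither guarantees mild or no impairment in every domain nor captures everyone who has it. The failure in the first direction covers 102 of 165 qualifying patterns, 12 of them with a Marked domain. In the other direction the only excluded pattern is 3/3/3. These counts assume whole-number items and that the bands apply to items, as the SAP says. How many participants would be affected cannot be derived from the documents.

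The consequence is limited. SAP 8.7.4 calls the SDS responder analysis exploratory, the rule applies identically to both arms, and other displays accompany it, including a cumulative distribution plot. The primary and key secondary tests, alpha and sample size are untouched. The point is still worth acting on because it changes what a reported rate means, at almost no cost.

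On the CAPS-5, all that is shown is a one-point difference between the protocol's cut-off of 11 and the upper end of the SAP's Asymptomatic band at 10. That is a matter to reconcile or explain.

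**What to change.** Before unblinding, amend SAP 8.7.4 in one of two ways:

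1. Define SDS functional remission as all three items at 3 or below, using the imputed item 1 where it applies. This fits the imputation rule: if items 2 and 3 are both 3 or below, so is their average.
2. Keep the mean rule, remove the statement that it indicates mild or no impairment, and report the all-items version beside it.

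The cost is a few lines of text and one derived variable. The downside is that the all-items remission rate may be lower than the mean-based one, since it drops 102 patterns and adds one.

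For the CAPS-5, add a sentence that either reconciles the protocol's remission cut-off with the SAP's bands or explains why the two differ by a point. Showing the rate at both 11 or less and 10 or less would also serve.
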